### **MRI: Other Parameters**

Individual data will be listed. The listing of such data will be collated with the other MRI data.

Descriptive statistics will be provided for raw data and changes (percent and absolute change) from baseline by treatment for each scheduled time for each side treated [left and right]. The average absolute change and average of the percent change for the left and right sides will also be provided.

Additional analyses may be performed as appropriate.

### **Biomarker Data**

Individual biomarker data will be listed.

Biomarker data will be summarized by treatment group and scheduled time for raw data and changes from baseline (absolute and/or percent). Graphical displays will also be provided (e.g. plot of mean  $\pm$  SEM).

### **CMAP for TA**

Individual CMAP for TA data will be listed.

CMAP data will be summarized by treatment group and scheduled time for raw data and changes from baseline (absolute and/or percent).

Additional analyses may be performed as appropriate.

#### **4.8.2.2. Open-Label Extension**

##### **MRI: TMV**

Individual data will be listed. The listing of such data will be collated with the data collected in the double-blind, placebo-controlled phase.

Descriptive statistics will be provided for raw data and changes (percent and absolute change) from the start of the open-label extension (Day 190) will be provided by treatment for each scheduled time and side treated as well as the average absolute change and average percent change from baseline for the left and right sides.

Additional analyses may be performed as appropriate.

##### **MRI: CCMV, FF, and CIMF**

Individual data will be listed. The listing of such data will be collated with the data collected in the double-blind, placebo-controlled phase.

Descriptive statistics will be provided for raw data and changes (percent and absolute change) from the start of the open-label extension (Day 190) will be provided by treatment for each scheduled time and side treated as well as the average absolute change and average percent change from baseline for the left and right sides.

Additional analyses may be performed as appropriate.

##### **MRI: Other Parameters**

Individual data will be listed. The listing of such data will be collated with the data collected in the double-blind, placebo-controlled phase.

Descriptive statistics will be provided for raw data and changes (percent and absolute change) from the start of the open-label extension (Day 190) will be provided by treatment for each scheduled time and side treated as well as the average absolute change and average percent change from baseline for the left and right sides.

Additional analyses may be performed as appropriate.

##### **Biomarker Data**

Individual biomarker data will be listed and will be collated with data from the double-blind period.

Descriptive statistics of raw data and changes from baseline will be summarized by treatment sequence and scheduled time. Pooled summaries across treatment sequences will also be provided. Such summaries may be accompanied by a plot of mean  $\pm$  SEM.

Additional analyses may be performed as appropriate.

#### 4.8.2.2.3. Open-Label vs. Double-Blind Placebo-Controlled Period

##### **MRI: TMV**

The effect of ACE-083 administered during the open-label extension compared to the treatment administered in the double-blind placebo-controlled phase will be examined for those receiving ACE-083 during the double-blind phase and separately for those receiving placebo during the double-blind phase by comparing the average percent change (left and right side) observed between Day 190 and pre-first treatment baseline (1st 6 months) and Day 358 versus Day 190 (2nd 6 months) using an ANCOVA model.

Covariates to be included into the model are SEQUENCE, CMT-TYPE, and BASELINE where:

- SEQUENCE represents the treatment sequence from double blind to open-label (ACE-083 → ACE-083 or Placebo → ACE-083)
- CMT-TYPE refers to the type of CMT (e.g. CMT1 or CMTX)
- BASELINE represents the baseline TMV from the double-blind period

Least squares estimates of the SEQUENCE effect and 90% confidence intervals will be provided.

If the Day 358 and/or Day 190 assessments have no missing data, then the above ANCOVA model will be used for analysis. If missing data is present, a standard multiple imputation with the above ANCOVA model will be used for analysis as described in [Section 4.11.1](#).

The statistical analysis described above will be done on the Per Protocol Set and will be considered primary. The analyses described above will also be repeated for the Full Analysis Set.

In addition, a line graph of the mean ± SEM of the percent change from baseline will be provided by sequence for each scheduled time.

Additional analyses may be performed as appropriate.

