10. TREATMENT OF PATIENTS

10.1. Treatments Administered

Using electromyography (EMG) or ultrasound guidance, each dose of study drug will be administered into the non-tendinous portion of the TA as a series of up to 4 equal-volume injections. The use of EMG or ultrasound guidance will ensure that viable muscle is present at the injection site. If the degree of atrophy or fibro-fatty infiltration poses administration challenges, injections of ACE-083 should be distributed approximately 2 cm apart into viable muscle. Injection site locations as well as measures to avoid adjacent nerves, blood vessels, and prevent intravascular injection are outlined in the IP Handling Guide.

The maximum absolute dose level and schedule, based on SRT review, is 250 mg/muscle administered bilaterally by injection into the left and right TA muscles every 3 weeks for up to 5 doses in Part 1 and up to 17 doses in Part 2.

For Part 2, ACE-083 or placebo (normal saline) will be administered blinded study drug every 3 weeks for approximately 6 months (9 doses). Patients who complete the double-blind treatment period will immediately roll over to open-label treatment with ACE-083, receiving the same dose of active drug, bilaterally in the TA muscle once every 3 weeks for approximately 6 months (8 doses).

The planned dose scheme for Part 1 and 2 is shown in Table 4.

Table 4:Cohort Schedule for Study A083-03

Part 1: N=U	o to 18 ((non-randomized, o	open-label, d	lose-escalation)
		(

Cohort	ACE-083 Dose per Muscle ^a	ACE-083 n
1	150 mg	6
2	TBD up to 200 mg ^b	6
3	TBD up to 250 mg ^b	6

Part 2: N= Up to 40 (6-month, randomized, double-blind, placebo-controlled, with 6-month open-label extension)

	6-month double contro	6-month open-label extension	
ACE-083 Dose per Muscle ^a	ACE-083 n	Placebo n	ACE-083 n
TBD up to 250 mg ^b	20	20	40

^a Administered bilaterally by injection into the tibialis anterior muscle once every 3 weeks

^b Dose level to be based on recommendations from the SRT

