For each pharmacodynamic variable, raw data and changes (percent and/or absolute change) from the start of the open-label extension (Day 190) will be summarized by treatment for each scheduled time using descriptive statistics.

Additional analyses may be performed as appropriate.

Open-label extension vs. double-blind placebo-controlled phase

For each of the following pharmacodynamic variables, a mixed model will be used to assess the effect ACE-083 administered during the open-label extension [Day 358 vs. Day 190 (2nd 6 months)] compared to the effect of the treatment administered in the double-blind placebo-controlled phase [Day 190 vs. pre-first treatment baseline (1st 6 months)] separately for those receiving placebo during the double-blind phase as well as for those receiving ACE-083 during the double-blind phase:

- Percent change in total muscle volume (average of right and left sides) during the openlabel extension vs. double-blind phase
- Percent change in intramuscular fat fraction (average of right and left sides) during the open-label extension vs. double-blind phase
- Percent change in contractile muscle fraction (average of right and left sides) during the open-label extension vs. double-blind phase
- Percent change in contractile muscle volume (average of right and left sides) during the open-label extension vs. double-blind phase

Least squares estimates of this effect and 95% confidence intervals will be provided. In addition, point estimates of this effect and corresponding 95% confidence intervals will be provided for patients having dorsiflexion MRC-MMT grade of 4- to 4+ on both sides.

Additional analyses may be performed as appropriate.

Clinical Study Protocol Study A083-03 Revision: 03 14.2.4.1. Pooled Analyses

If applicable, similar analyses will be performed for pooled Part 1 and 2 data for patients at the same dose level. Pooling by the estimated local dose of ACE-083 in the injected muscle (i.e., mg ACE-083/g muscle) may also be performed. Details of these analyses will be included in the SAP.

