**Table 1: Planned Doses to be Administered for Part 1**

Cohort	Dosing Days	Muscle	Planned Dose Level	Type of Administration	ACE-083 n
1	1, 22, 43, 64, and 85	Tibialis Anterior	150 mg	Bilateral	6
2	1, 22, 43, 64, and 85	Tibialis Anterior	200 mg	Bilateral	6
3	1, 22, 43, 64, and 85	Tibialis Anterior	240 mg	Bilateral	6
Total Number of Patients (Planned)					18

Periodic reviews of selected blinded safety and imaging data will be reviewed by the Safety Review Team (SRT) in accordance with the SRT Guidelines.

#### 3.2. Part 2

Prior to the initiation of Part 2, a review of the safety and efficacy data from Part 1 will be done in order to determine the recommended dose level. Up to 40 patients will be enrolled and randomized (1:1 ratio) to receive either ACE-083 (n=20) or placebo (n=20) bilaterally. Patients will receive study drug once every three weeks for approximately 6 months (9 doses). If a patient discontinues the study for reasons other than a safety issue related to investigational study drug and the patient had not completed the Day 43 visit, the patient may be replaced. The replacement patient will receive the same treatment as the patient replaced.

Patients who complete the double-blind treatment period will immediately roll over to open-label treatment with ACE-083. All patients will receive ACE-083 administered at the same dose as in the double-blind period. They will receive bilateral injections, once every three weeks for approximately 6 months (8 doses). In Part 2, the SRT will periodically review the blinded safety data.

A stratified randomization schedule will be prepared under the direction of the Sponsor with the stratification factor of “CMT disease type” (values are CMT1 and CMTX). Because Part 2 is multicenter, an Interactive Response Technology (IRT) system will be used to randomize patients sequentially across clinical sites.

Similar to Part 1, periodic reviews of selected blinded safety and imaging data will be reviewed. Further details concerning the frequency and timing of SRT reviews of Part 2 data are described in the SRT Guidelines.

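### The open-label versus double-blind comparison sets 27 weeks and 9 doses against 24 weeks and 8 doses, both called six months, with no adjustment; the distortion is about 11% if gain accrues evenly per dose and small if the effect plateaus

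*SAP*

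**What the plan says.** Protocol 14.2.4 names the two windows as "Day 190 vs. pre-first treatment baseline (1st 6 months") and "Day 358 vs. Day 190 (2nd 6 months"). Protocol 14.2.3 uses the same pair for efficacy. SAP 4.8.2.2.3 carries this into an ANCOVA for total muscle volume, "by comparing the average percent change (left and right side) observed between Day 190 and pre-first treatment baseline" and between Day 190 and Day 358. It does so for patients on ACE-083 throughout and, separately, for those who began on placebo. The covariates are SEQUENCE, CMT-TYPE and BASELINE, and the reported quantity is the SEQUENCE effect. There is no period term, offset or scaling for length.

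SAP 4.7.2.2.3 repeats the windows for MVIC, MRC-MMT, the 10-meter and 6-minute tests, Berg, CMT-HI, CMTES2 and gait. Falls is the exception: it uses Weeks 1 to 24 and Weeks 25 to 48, with a PERIOD covariate.

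The dose counts are printed openly. Protocol 10.1 gives "every 3 weeks for approximately 6 months (9 doses") for the double-blind period and "once every 3 weeks for approximately 6 months (8 doses") for the extension. SAP 3.2 gives the same counts. SAP 4.1.4 makes Day 190 the baseline for open-label assessments. SAP Section 5, which lists departures from the protocol, does not mention window length.

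**The concern.** The comparison asks two questions. In patients on ACE-083 throughout, does the second period add as much as the first? In patients who switch from placebo, how does the change on drug compare with their own change on placebo? Both are within-patient comparisons of two changes, and both need windows of like length and exposure. Here the first window is three weeks longer and holds one more dose, while the shared label tells the reader that they match. A shortfall in the second period could then be read partly as fading benefit, or the gain after switching could look a little smaller, because of the calendar. More patients would not remove such a difference.

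**Working it through.** **Windows and doses.** Inputs are the Part 2 schedule (Protocol Table 6) and the exposure formula in SAP 4.6.1, (last dose − first dose + 21)/7.
- Double-blind doses fall on Days 1, 22, 43, 64, 85, 106, 127, 148 and 169: 9 doses, as printed. Exposure is (169 − 1 + 21)/7 = 27 weeks; 190 − 1 = 189 days.
- Open-label doses fall on Days 190, 211, 232, 253, 274, 295, 316 and 337: 8 doses, as printed. Exposure is (337 − 190 + 21)/7 = 24 weeks; 358 − 190 = 168 days.
- At the SAP's 30.417 days per month these are 6.21 and 5.52 months. The ratio is 24/27 = 8/9 = 0.889.

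**Even accrual per dose.** Take the design difference of 10 points (SAP 4.1.1) as the gain over 9 doses. Eight doses give 10 × 8/9 = 8.89 points, a shortfall of 1.11 points or 11.1%. For gains of 5 and 15 points the shortfall is 0.56 and 1.67.

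**Against sampling error.** With the design SD of 10, n = 20 in a sequence and an assumed between-period correlation ρ, SE = 10 × √(2(1 − ρ)/20).
- ρ = 0: SE 3.16, so 1.11/3.16 = 0.35.
- ρ = 0.5: SE 2.24, ratio 0.50.
- ρ = 0.8: SE 1.41, ratio 0.79.

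**Saturating accrual.** Let E(t) = 1 − exp(−kt), scaled to 10 points at 27 weeks, with assumed half-times. The second-period change in patients on ACE-083 throughout would be:

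| Half-time (weeks) | 24-week window | 27-week window | 24/27-week ratio |
|---|---|---|---|
| 4 | 0.09 | 0.09 | 0.994 |
| 9 | 1.20 | 1.25 | 0.963 |
| 26 | 4.48 | 4.87 | 0.921 |
| 52 | 6.32 | 6.98 | 0.906 |

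The same ratio applies to the on-drug change after switching from placebo. With a short half-time the second-period change is near zero for either window, and the missing three weeks explain almost none of it.

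**Between-sequence contrast.** Let the outcome be period 2 minus period 1, with linear rates r on drug and p on placebo. Then (24r − 27r) − (24r − 27p) = −27(r − p). With r = 10/27 and p = 0 this is −10.0 points, the same as with two 27-week windows. The mismatch cancels.

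**Denominator, a separate effect.** A percent change taken on the Day 190 value divides by 110 rather than 100. A second gain of 10 points over an equal 27-week window would read 10/110 = 9.09%, about 9% smaller. Both effects together give 8.89/110 = 8.08%, about 19% smaller, of which only 11% is due to window length.

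**Matched windows.** 106 − 1 = 105 days and 295 − 190 = 105 days, with 5 doses in each and the end assessment three weeks after the fifth. Under even accrual each gains 10 × 5/9 = 5.56 points of original baseline. On the Day 190 denominator the second would read 5.56/110 = 5.05%, still 9% smaller, so matching the windows is not enough without a common denominator.

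**The case against.** A reader might infer that a constant drug effect must appear to weaken in the extension. The documents do not support that. It requires even gain per dose, and neither document states an accrual shape. The only evidence on shape points away from it: Protocol 7.2 reports an 8.9% rise in TA volume after two Phase 1 doses, which would extrapolate linearly to 8.9 × 9/2 = 40% after nine, against a planning difference of 10 points. The population differs, so this is indicative only. A reader might also attribute the whole 19% to the windows, but about half of it is the denominator.

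The reported quantity matters too. If the SEQUENCE effect is a between-sequence contrast of period differences, the mismatch cancels under linear accrual. The SAP does not define the dependent variable well enough to tell. It does say that each sequence is examined separately, and for the other MRI parameters it compares the two periods descriptively by sequence. In those within-sequence readings the mismatch remains.

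Much is already visible. Dose counts are printed, each period is called approximately six months, exposure in weeks is summarized by period, and changes at every scheduled visit will be tabulated. This limits the harm, but a reader must still reconstruct the mismatch, and no like-for-like contrast is planned. Replacing the full-period comparison with a 15-week one would discard Days 106 to 190 and 295 to 358, so the matched contrast should be added rather than substituted.

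**Conclusion.** The within-sequence comparison is not like for like, and nothing in either plan adjusts for it outside Falls. Under even accrual per dose the second-period change is understated by 11% (1.11 points at the design effect, 0.35 to 0.79 SE at n = 20, SD 10 and assumed correlation 0 to 0.8). Under a plateau the window distortion is small: below 0.1 point for half-times of 4 and 9 weeks. In a between-sequence contrast of period differences it is nil under linear accrual. The further 9% shrinkage for percent-change endpoints is a denominator effect. This is a secondary comparison; the primary Day 190 test and the sample size are untouched. The point is a cheap improvement, not a threat to the trial's main conclusion.

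**What to change.** In SAP 4.7.2.2.3 and 4.8.2.2.3:
- Keep the Day 190/Day 358 comparison, but label it 27 weeks and 9 doses versus 24 weeks and 8 doses.
- Add a matched contrast of baseline to Day 106 versus Day 190 to Day 295 for MRI, strength, timed tests, balance and gait, CMTES2 and CMT-HI, all of which Protocol Table 6 schedules at Days 106, 190 and 295.
- For percent-change endpoints, express both changes on the pre-first-dose baseline.
- Use per-dose scaling (dividing by 9 and by 8) at most as a sensitivity analysis, because it assumes linear accrual.

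State the limits. The matched window covers only 15 weeks. The Day 1 MRI may be taken up to 14 days early. CMT-HI has no Day 1 assessment in Table 6, so its baseline is the screening value (Day −28 to −7), making its first matched window about 16 to 19 weeks. In both cases the doses still match at five each. MRC-MMT has no Day 106 value and can only have the labelled full-period comparison.

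The cost is SAP wording and one additional set of model runs, with no new visits or data.

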For the MVIC value and decimal MMT-MRC score for each side treated as well as the average from the left and right sides, CMTES2 score, CMT-HI total score and selected subscale scores, and motor function test assessments, raw data and changes from baseline (percent and absolute change) from baseline will be summarized by treatment for each scheduled time using descriptive statistics. In addition, a mixed model will be fitted to assess the treatment effect (ACE-083 vs. placebo) using a 2-sided 0.10 significance level for the percent change from baseline. Least squares estimates of the treatment effect and corresponding 90% confidence intervals will be provided. In addition, least squares estimates of the treatment effect and corresponding 90% confidence intervals will be provided for patients having dorsiflexion MMT-MRC grade of 4- to 4+ on both sides.

Additional analyses may be performed as appropriate.

Open-label extension

For the MVIC value and decimal MMT-MRC score for each side treated as well as the average from the left and right sides, CMTES2 score, CMT-HI total score and selected subscale scores, and motor function test assessments, raw data and changes (percent and absolute change) from the start of the open-label extension (Day 190) will be summarized by treatment for each scheduled time using descriptive statistics.

Additional analyses may be performed as appropriate.

Open-label extension vs. double-blind placebo-controlled phase

For the MVIC value [average from the left and right sides] decimal MMT-MRC score [average from the left and right sides], CMTES2 score, CMT-HI total score and selected subscale scores, and motor function test assessments, the effect of ACE-083 administered during the open-label extension compared to the treatment administered in the double-blind placebo-controlled phase will be examined for those receiving ACE-083 during the double-blind phase and separately for those receiving placebo during the double-blind phase by comparing the absolute and/or percent

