ACE-083 **Clinical Study Protocol** Study A083-03 Revision: 03 changes [depending on the parameter] observed between Day 190 and pre-first treatment baseline (1st 6 months) and Day 358 versus Day 190 (2nd 6 months) using a mixed model. Least squares estimates of this effect and 95% confidence intervals will be provided. In addition, least squares estimates of this effect and corresponding 95% confidence intervals will be provided for patients having dorsiflexion MRC-MMT grade of 4- to 4+ on both sides.

Additional analyses may be performed as appropriate.

14.2.4. **Pharmacodynamic Data**

Part 1

Individual pharmacodynamic data will be listed. For individual pharmacodynamic data that is measured on the left and right side (i.e., MRI), the average of the left and right side assessments will also be listed and summarized.

Descriptive statistics (change from baseline [percent and absolute change]) will be provided by treatment group and scheduled time. In addition, for muscle volume and intramuscular fat fraction, a repeated measures ANCOVA will be fitted to the percent change from baseline data and estimates of the effect of ACE-083 at 3 weeks post last dose and corresponding 90% confidence intervals will be provided.

Additional analyses may be performed as appropriate.

Part 2

Individual pharmacodynamic data will be listed. For individual pharmacodynamic data that is measured on the right and left side (i.e., MRI), the average of the left and right side assessments will also be listed and summarized.

Double-blind, placebo-controlled phase

Descriptive statistics for raw data and changes from baseline (percent and/or absolute change) will be provided for each pharmacodynamic parameter by treatment group for each scheduled time. For pharmacodynamic parameters that are measured on the right and left side (i.e., MRI), the descriptive statistics will include summaries for each side and the average of the right and left sides.

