14.5. Deviation from Original Analysis Plan

A formal statistical analysis plan for the analysis and presentation of data from this study will be prepared before the database lock. Deviations from the statistical analyses outlined in this protocol will be indicated in this plan; any further modifications will be noted in the final clinical study report.

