##### **Muscle Strength [Maximum voluntary isometric contraction {MVIC}]**

Individual MVIC data will be listed.

Descriptive statistics of the raw data as well as the absolute and percent change from baseline will be provided by side treated [left and right]. The average absolute and average percent change from baseline for the left and right sides will also be provided.

Least squares mean estimates of the effect of ACE-083 and corresponding 90% and 95% confidence intervals will be produced for the average percent change data (left and right sides) at 3-weeks post last dose [theoretically the Day 106 assessment] described above using an analysis of covariance (ANCOVA) with BASELINE, COHORT, BASELINE\*COHORT, and CMT-TYPE as covariates where:

- COHORT represents the dose level of ACE-083 administered to the muscle
- BASELINE represents the baseline value (average for the left and right sides)
- BASELINE\*COHORT represents the interaction of the baseline and cohort
- CMT-TYPE refers to the type of patient (e.g. CMT1 or CMTX)

Additional analyses may be performed as appropriate.

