### **Falls**

The hazard ratio of recurring falls between ACE-083 and placebo during the entire 12 months (excluding the screening interval) will be estimated using the Andersen-Gill recurrent events model with the following covariates: SEQUENCE, CMT-TYPE, PERIOD, and ankle dorsiflexion MRC-MMT decimal score where SEQUENCE refers to the treatment sequence from double-blind to open-label (ACE-083  $\rightarrow$  ACE-083 or Placebo  $\rightarrow$  ACE-083), and PERIOD

refers to the period of time of observation (“Double-blind”, “Open-label”). The “Double-Blind” period covers Weeks 1 to 24 and the “Open-label” period covers Weeks 25 to 48. The point estimate, p-value and 90% confidence interval for the hazard ratio for SEQUENCE will be provided.

Additional methods for the statistical analysis of the recurring event of falls may be considered and performed as appropriate (e.g. negative binomial regression with similar covariates as listed for the Andersen-Gill recurrent events model described above).

No multiple imputations will be performed for missing data.

The statistical analyses described above will be done on the Per Protocol Set and will be considered primary. The analyses described above will also be repeated for the Full Analysis Set.

Additional analyses may be performed as appropriate.

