## 5. MODIFICATIONS FROM THE STATISTICAL SECTION OF THE PROTOCOL

The following modifications from the statistical section of the protocol have been implemented in the statistical analysis plan:

- For statistical analyses where confidence intervals for the least-squares mean are provided, the 95% confidence interval will be provided in addition to the 90% confidence interval.
- The “Safety Population” is now called the “Safety Set”.
- The “Per Protocol Set” definition was redefined to be what is listed in this document..
- The last observation carried forward approach is not being performed in the statistical analyses. Standard multiple imputation will be performed to assess the impact of missing data on the observed data.
- For statistical analyses of data to compare the effects of ACE-083 administered in the open-label extension versus the treatment received in the double-blind period of Part 2, the 90% confidence interval will be provided in place of the 95% confidence interval.

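### Supplementary open-label versus double-blind analyses: the ANCOVA response is undefined, the 12-month falls ratio is mislabelled, and a falls boundary and a baseline covariate are wrong (minor)

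*SAP*

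**What the plan says.** Protocol 14.2.3 says that the effect of open-label ACE-083 relative to the double-blind treatment "will be examined for those receiving ACE-083 during the double-blind phase and separately for those receiving placebo during the double-blind phase". It compares the change from baseline to Day 190 with "Day 358 versus Day 190 (2nd 6 months) using a mixed model", and the output is "Least squares estimates of this effect and 95% confidence intervals will be provided". Protocol 14.2.4 asks for the same comparison for four MRI variables.

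SAP 4.7.2.2.3 and 4.8.2.2.3 take this up under ten headings: MVIC, MRC-MMT score, 10-meter walk/run, 6-minute walk, Berg, CMT-HI, CMTES2, gait, TMV, and CCMV/FF/CIMF together. Each names both six-month changes and uses an ANCOVA with SEQUENCE, CMT-TYPE and BASELINE; some add height or MRC-MMT score. The promised model output is "Least squares estimates of the SEQUENCE effect and 90% confidence intervals will be provided". The gait model names only patients who started on ACE-083, yet keeps SEQUENCE as covariate and reported effect.

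For falls, SAP 4.7.2.2.3 says "The hazard ratio of recurring falls between ACE-083 and placebo during the entire 12 months (excluding the screening interval) will be estimated" with an Andersen-Gill model containing SEQUENCE and PERIOD. The ratio it reports is the one for SEQUENCE. SAP 3.2 has all patients on ACE-083 in the extension. The falls sections (4.7.1.2, 4.7.2.2.2 and 4.7.2.2.3) begin the open-label period at Week 25, while SAP 4.1.5 identifies the Day 190 dose as the first open-label dose.

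For CCMV, FF and CIMF, SAP 4.8.2.2.3 defines BASELINE as baseline TMV. The double-blind analysis of the same variables (4.8.2.2.1) uses each parameter's own baseline.

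On departures from the protocol, Protocol 14.5 says "Deviations from the statistical analyses outlined in this protocol will be indicated in this plan". For this comparison SAP section 5 lists only that "the 90% confidence interval will be provided in place of the 95% confidence interval".

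**The concern.** An ANCOVA needs a stated response. Here two changes per patient are named, but the text does not say whether they enter as a difference, as stacked rows, or through the second change alone. A SEQUENCE effect is ordinarily read as a contrast between the two sequences, whereas the protocol asks for one effect within each former arm. Two programmers could therefore report different quantities from the same text, and one of those quantities does not answer the protocol's question.

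The falls wording has a separate problem. There is no placebo group from Day 190, so a 12-month sequence ratio presented as ACE-083 versus placebo would be misdescribed in the report. The Week 25 boundary would also put double-blind time into the open-label fall counts, and the TMV covariate is less relevant to the three variables it adjusts.

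**Working it through.** **Planning figure.** This point disputes no stated figure. The one planning input used is the 10-point difference in SAP 4.1.1. With SD 10 and two-sided alpha 0.10, 18 per arm gives power 0.902 by the exact t-test, so the plan's 36 reproduces.

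**Can a between-sequence contrast give the within-arm effects?** Take double-blind TMV changes of 10 (ACE-083) and 0 (placebo), and call the open-label changes a for ACE-083-first and p for placebo-first. The values of a and p are assumed. The within-arm effects (second change minus first) are a − 10 and p − 0. The contrast, ACE-083-first minus placebo-first, depends on the response:

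- difference of changes: (a − 10) − p
- open-label change alone: a − p
- both changes stacked: (10 + a)/2 − (0 + p)/2

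| (a, p) | Within-arm effects | Difference | Second change | Stacked |
|---|---|---|---|---|
| (0, 5) | −10, +5 | −15 | −5 | +2.5 |
| (3, 8) | −7, +8 | −15 | −5 | +2.5 |
| (5, 10) | −5, +10 | −15 | −5 | +2.5 |

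Three different pairs of within-arm effects give one contrast under each response. The least squares mean for each sequence on the difference response recovers each pair. If the model is instead fitted separately by former arm, SEQUENCE is constant (design rank 3 with 4 columns) and its effect cannot be estimated.

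**Falls ratio.** Assume a constant placebo hazard of 1 per week, a sustained on-drug ratio of 0.50, no dropout and no covariate effects. With equal risk sets the Andersen-Gill ratio is the ratio of expected counts. Let placebo patients cross over after w weeks and let the effect begin L weeks after starting drug. Then over 48 weeks:

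ratio = [L + 0.5(48 − L)] / [(w + L) + 0.5(48 − w − L)]

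Use w = 27 for crossover at Day 190 and w = 24 for crossover after Week 24. With L = 0 these give 24/37.5 = 0.64 and 24/36 = 0.67. The Weeks 1 to 24 ratio in SAP 4.7.2.2.1 would be (12 + 0.5L)/24.

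| Lag (weeks) | 48-week SEQUENCE ratio (w = 27 to 24) | Weeks 1 to 24 ratio |
|---|---|---|
| 0 | 0.64 to 0.67 | 0.50 |
| 8 | 0.68 to 0.70 | 0.67 |
| 12 | 0.69 to 0.71 | 0.75 |

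The order of the two ratios reverses at a lag of about 8.5 weeks (w = 27) to 9.9 weeks (w = 24).

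**Boundary.** Week k starts on Day 7(k − 1) + 1. Week 25 starts on Day 169, the ninth and last double-blind dose; Week 28 starts on Day 190. Planned Days 169 to 189 are therefore double-blind time: 3 of 24 weeks, or 12.5% of the labelled open-label period. With an immediate ratio of 0.50, the placebo-first open-label fall rate would read (3 + 21 × 0.5)/24 = 0.56 of the placebo rate instead of 0.50.

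**Covariate.** Setting SAP 4.8.2.2.3 beside 4.8.2.2.1 shows the mismatch directly. It bears on precision, and the documents give nothing from which to quantify it.

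**The case against.** The best defence is that the SAP means the difference of the two changes and will report a least squares mean for each sequence. Much of this stands. Both changes are named, so analysing only the second would contradict the text. Where the SAP wants repeated rows it specifies an MMRM with VISIT and TREATMENT*VISIT, so stacking fits poorly. The separate-by-arm aim is repeated under every heading except the gait model. Unlike the Day 190 analysis, no test level is attached to SEQUENCE. The SAP also uses effect language for least squares means where there is no control group: in Part 1, "Least squares mean estimates of the effect of ACE-083 and corresponding 90% and 95% confidence intervals will be produced". By-sequence line graphs are planned for most of these endpoints. A reader might infer that the SAP has replaced the protocol's question with a between-sequence contrast; the documents do not support that. What remains is that neither the response nor the per-sequence output is written down.

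For falls, the SAP defines SEQUENCE and says that its ratio is reported, so only the introductory description is wrong. A reader might also infer that the 12-month ratio always understates the effect relative to the double-blind ratio. That does not follow, because the direction depends on a lag the documents do not give.

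Nor does the Week 25 boundary distort the SEQUENCE ratio. On study time, a PERIOD term that switches at the same week for everyone is absorbed by the baseline hazard.

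The unlisted move from mixed model to ANCOVA is not peculiar to this comparison. It applies equally to the primary analysis (Protocol 14.2.4 against SAP 4.8.2.2.1), so it is housekeeping here.

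**Conclusion.** The point holds, as a minor one. The open-label versus double-blind ANCOVAs are ambiguous: the difference response is the most natural reading and would answer the protocol's question, but it is not stated. Three details are wrong as written:

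- the description of the 12-month falls ratio;
- the start of the open-label falls period, which takes in 3 double-blind weeks out of 24 and affects the period fall counts;
- the baseline covariate for CCMV, FF and CIMF, which affects precision by an unknown amount.

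The 0.64 to 0.67 figure rests on constant hazards, no lag and no dropout, and the TMV figures use assumed open-label changes. All are illustrations, not predictions. These analyses are supplementary, falls are exploratory, and the Day 190 primary analysis of TMV is unaffected.

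**What to change.** 1. In the ten ANCOVA subsections of SAP 4.7.2.2.3 and 4.8.2.2.3, define the response as each patient's Day 190 to Day 358 change minus the baseline to Day 190 change. Report the least squares mean and 90% confidence interval for each sequence.
   - For the MRC-MMT outcome, keep only one of MRC-MMT SCORE and BASELINE. The only scheduled pre-dose MMT is at Screening (Protocol Table 6), so they are the same variable.
   - For mid-swing foot angle, include both former arms and keep SEQUENCE.
2. In the 12-month falls analysis, label the ratio ACE-083→ACE-083 versus Placebo→ACE-083. Refer to the double-blind falls analysis in SAP 4.7.2.2.1 for ACE-083 versus placebo.
3. Set the falls boundary at the first open-label dose in all four places: SAP 4.7.1.2, 4.7.2.2.1, 4.7.2.2.2 and 4.7.2.2.3. Weeks 25 to 27 then count as double-blind time. Changing only some of these sections would leave those weeks in neither period.
4. For CCMV, FF and CIMF in SAP 4.8.2.2.3, use the analysed parameter's own baseline.
5. As housekeeping, list the change from mixed model to ANCOVA in SAP section 5.

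The cost is SAP wording and minor programming. No new data are needed.
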